3.1.1.3 Overall visit response

Table 2 defines how the previously defined TL and NTL visit responses will be combined with new lesion information to give an overall visit response.

Table 2 Overall visit response

Target Lesion	Non-target Lesion	New lesion(s)	Overall response
CR	CR	No	CR
CR	NA	No	CR
NA	CR	No	CR
CR	Non CR/Non PD	No	PR
CR	NE	No	PR
PR	Non PD or NE	No	PR
SD	Non PD or NE	No	SD
NA	Non CR/Non PD	No	SD (Non CR/Non PD)
NE	Non PD or NE	No	NE
NA	NE	No	NE
PD	Any	Yes or No	PD
Any	PD	Yes or No	PD
Any	Any	Yes	PD
NA	NA	No	NED

CR = complete response, PR = partial response, SD = stable disease, PD = progressive disease, NE = not evaluable, NED = no evidence of disease, NA = not applicable (only relevant if there were no TL/NTL at baseline).

3.2 Efficacy outcome variables

Following approval of CSP version 2.0 tumour based efficacy assessments will not be collected for Group A patients.

3.2.1 Progression free survival landmark summary

The endpoint PFS, as assessed by the investigator, using RECIST 1.1 will be reported both with and without **confirmation of progression**. will be defined as the time from the date of randomisation until the date of the first objective disease progression or death (by any cause in the absence of progression) regardless of whether the patient withdraws from randomised therapy or receives another anti-cancer therapy prior to progression (i.e., date of PFS event or censoring – date of randomisation + 1).

Patients who have not progressed or died at the time of summary will be censored at the time of the latest date of assessment from their last evaluable RECIST 1.1 assessment. However, if

the patient progresses or dies after 2 or more missed visits, the patient will be censored at the time of the latest evaluable RECIST 1.1 assessment prior to the two missed visits with the exception of 2 missed visits from baseline (i.e. if the subject dies within 119 days of the last evaluable visit), the event of death will be used in the PFS summary).

Given the scheduled visit assessment scheme (i.e. eight-weekly for the first 48 weeks then twelve-weekly thereafter) the definition of 2 missed visits will change. If the previous RECIST assessment is less than study day 232 (i.e. week 32 + 7 day visit window) then two missing visits will equate to 17 weeks (2 x 8 week scans + 7 day visit window) since the previous RECIST assessment, allowing for late visits.

If the two missed visits occur over the period when the scheduled frequency of RECIST assessments changes from eight-weekly to twelve-weekly this will equate to 21 weeks. The time period for the previous RECIST assessment will be from study day 287. From week 49 (week 48 + 7 days) onwards, two missing visits will equate to 25 weeks (2 x 12 week scans + 7 day visit window).

If the patient has no evaluable visits or does not have baseline data they will be censored at baseline unless they die within 112 days of baseline (2 x 8 week scans).

The PFS time will always be derived based on scan/assessment dates not visit dates.

RECIST 1.1 assessments/scans contributing towards a particular visit may be performed on different dates. The following rules will be applied:

- For investigational assessments, the date of progression will be determined based on the earliest of the RECIST assessment/scan dates of the component that indicates progression

Note: For TLs, only the latest scan date is recorded out of all scans performed at that assessment for the TLs and similarly for NTLs only the latest scan date is recorded out of all scans performed at that assessment for the NTLs. Additionally, PFS will be obtained using the algorithm described above for the RECIST site investigator tumour data. An additional sensitivity summary using a modified version of the algorithm will be used, whereby any objective disease progression must be **confirmed by** the next scheduled scan. The **confirmatory** scan must be no sooner than 4 weeks after the initial suspected progression. If disease progression is **confirmed** (or disease progression occurs and no further scans are recorded) then the date of progression will be when it was originally observed. Patients with a single disease progression and no further tumour assessment scans will be treated as PD in the summary.

The proportion of patients alive and progression free at 6 months (i.e., APF6) will be defined as the Kaplan-Meier (KM) estimate of PFS at 6 months.

The proportion of patients alive and progression free at 12 months (i.e., APF12) will be defined as the KM estimate of PFS at 12 months.

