3. PRIMARY AND EXPLORATORY VARIABLES

3.1 Derivation of RECIST visit responses

All RECIST assessments, whether scheduled or unscheduled, will be included in the calculations. This is also regardless of whether a patient discontinues study drug.

For all patients, the RECIST version 1.1 (see further Appendix C of the CSP) tumour response data will be used to determine each patient's visit response. It will also be used to determine if and when a patient has progressed and also their best overall response.

The baseline tumour assessment is part of the screening procedures and should be performed within 28 days before the start of study treatment.

Prior to approval of CSP version 2.0, efficacy for all patients will be assessed by objective tumour assessments every 8 weeks (relative to the first dose) for the first 48 weeks, then every 12 weeks thereafter, until confirmed objective disease progression as defined by RECIST 1.1 (irrespective of the reason for stopping study drug and/or subsequent therapy). For patients who discontinue study drug due to toxicity or a reason other than confirmed progression of disease (PD), objective tumour assessments should be continued every 8 weeks for 48 weeks (relative to first dose) then every 12 weeks thereafter until confirmed objective disease

progression. If an unscheduled assessment is performed, and the patient has not progressed, every attempt should be made to perform the subsequent assessments at their scheduled visits. Patients on monotherapy AZD9291 will be assessed according to local practice until objective disease progression.

Disease progression requires confirmation, the confirmatory scan should occur preferably at the next scheduled visit and no earlier than 4 weeks after the initial assessment of PD in the absence of clinically significant deterioration. Study treatment will continue between the initial assessment of progression and confirmation for progression.

Progression would be considered confirmed if the following criteria are met:

- $\geq 20\%$ increase in the sum diameters of target lesions (TLs) compared with the nadir at 2 consecutive visits with an absolute increase of at least 5 mm.

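### SAP 3.2.1: the day bounds for two missed visits do not fit the scan schedule at weeks 40 and 48, and early deaths have two conflicting limits (112 and 119 days)

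*SAP*

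**What the plan says.** SAP 3.1 schedules scans "every 8 weeks (relative to the first dose) for the first 48 weeks, then every 12 weeks thereafter", so visits fall at weeks 8, 16, 24, 32, 40, 48, 60, 72 and so on. It adds: "All RECIST assessments, whether scheduled or unscheduled, will be included in the calculations".

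SAP 3.2.1 censors a progression or death that follows two or more missed visits at the last evaluable scan before the gap. It gives three limits:

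- 17 weeks: "If the previous RECIST assessment is less than study day 232 (i.e. week 32 + 7 day visit window".
- 21 weeks, when the missed visits fall where "the scheduled frequency of RECIST assessments changes from eight-weekly to twelve-weekly this will equate to 21 weeks". The day bound follows: "The time period for the previous RECIST assessment will be from study day 287". No end day is given.
- 25 weeks: "From week 49 (week 48 + 7 days) onwards, two missing visits will equate to 25 weeks".

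For early deaths, 3.2.1 makes an exception for two missed visits from baseline: "if the subject dies within 119 days of the last evaluable visit", the death counts. A later sentence, on patients with no evaluable visits or no baseline data, says "they will be censored at baseline unless they die within 112 days of baseline (2 x 8 week scans".

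SAP 3.2.5 assigns best overall response (BOR) for deaths without an evaluable assessment. It uses 17 weeks in two branches, counted from randomisation in the first and from first dose in the second. SAP 4.1.2 sets Study Day 1 for efficacy at randomisation.

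**The concern.** These limits decide whether a patient is an event or is censored, and three things do not fit.

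1. The 21-week wording describes a previous scan at week 40, but its day bound starts where the week-40 window ends. A program keyed to the day bounds has no rule for days 232–286.
2. The week-49 clause does not say whether it refers to the previous scan or to the missed visits. The two readings classify the same week-48 patient differently.
3. Two early-death limits apply to a patient with only a baseline scan. Together with 3.2.5, the text uses four start points: last evaluable visit, baseline, randomisation and first dose.

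Two programmers could follow the SAP and produce different PFS data. Duration of response (DoR) is affected too, because 3.2.3 ends it at the PFS event or censoring date.

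**Working it through.** **Inputs.** Visit weeks from 3.1. Study day from 4.1.2: week w falls on day 7w + 1, assuming first dose on the day of randomisation. Window of ±7 days (3.2.1 allows 7 days; 3.2.5 uses 16 weeks ± 1 week).

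**The SAP's own figures.** The lengths reproduce: 8 + 8 + 1 = 17 weeks (119 days), 8 + 12 + 1 = 21 weeks (147 days), 12 + 12 + 1 = 25 weeks (175 days). Day 232 = 32 × 7 + 7 + 1 also reproduces. Day 287 = 40 × 7 + 7 reproduces only as the end of the week-40 window.

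**Bounds against the schedule**, with the week-49 clause read as the previous scan:

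| Previous scan | Day (window) | Next two visits | Limit needed | Limit from the day bounds |
|---|---|---|---|---|
| Week 32 | 225 (218–232) | 40, 48 | 17 weeks | 17 weeks; day 232 itself excluded |
| Week 40 | 281 (274–288) | 48, 60 | 21 weeks | none on 274–286; 21 on 287–288 |
| Week 48 | 337 (330–344) | 60, 72 | 25 weeks | 21 on 330–343; 25 on 344 |
| Week 60 | 421 (414–428) | 72, 84 | 25 weeks | 25 weeks |

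**Week 40.** Days 232 to 286 are 286 − 232 + 1 = 55 days without a day band. They include 13 of the 15 days in the week-40 window. The 21-week wording still covers week 40. It does not cover a scan on days 232–273, whose next two visits (weeks 40 and 48) are both eight-weekly. If a program defaulted to 17 weeks for an on-time week-40 scan, the limit would be 281 + 119 = day 400, before the week-60 visit on day 421, so one missed visit would censor.

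**Week 48.** Take a scan on day 337, week 60 missed, and progression on time at week 72 (day 505). The gap is 505 − 337 = 168 days.

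- Clause read as the previous scan: the limit is 147 days. Since 168 > 147, PFS is censored at day 337 after one missed visit.
- Clause read as the missed visits: the limit is 175 days. Since 168 < 175, PFS is an event at day 505. The open-ended day-287 bound still covers day 337, so the two rules overlap.

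With first response on day 57, DoR is 505 − 57 + 1 = 449 days with an event, or 337 − 57 + 1 = 281 days censored.

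**Early deaths.** For a patient with only a baseline scan, a death 113–119 days after baseline is an event under the 119-day sentence and is censored at baseline under the 112-day sentence.

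Let the baseline scan fall b days before randomisation. SAP 3.1 allows up to 28 days before treatment, so b = 0 to 28 with first dose on the day of randomisation. If baseline means the scan date, the limits from randomisation become 112 − b and 119 − b, against 119 for BOR. BOR is then PD while PFS is censored for deaths at:

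- 113 − b to 119 days after randomisation under the 112-day sentence (7 to 35 days wide);
- 120 − b to 119 days under the 119-day sentence (0 to 28 days wide).

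Censoring at the scan date gives a PFS time of 1 − b days, down to −27. In 3.2.5, if first dose is d days after randomisation, deaths 120 to 119 + d days after randomisation fall in neither BOR category.

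**Effect on the 6-month estimate (APF6).** Assume n patients in the arm, k other events by 6 months and no other censoring. Counting the death gives (n − 1 − k)/n. Censoring it at baseline gives (n − 1 − k)/(n − 1).

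| n | k | Event | Censored | Difference |
|---|---|---|---|---|
| 14 | 0 | 92.9% | 100.0% | 7.1 points |
| 15 | 3 | 73.3% | 78.6% | 5.2 points |
| 15 | 7 | 46.7% | 50.0% | 3.3 points |

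**The case against.** The best defence is that the words, not the day numbers, should govern. They give week 40 its 21 weeks. After a week-48 scan the missed visits are both twelve-weekly, so the 21-week condition fails, and the grammatical subject of the week-49 clause is the missing visits. The general rule also requires two missed visits, and the worked patient missed one. This is a fair reading, and it makes week 48 an ambiguity, not a certain error. It does not remove the problem: the two preceding rules are keyed to the previous scan, and the day-287 bound has no end.

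On early deaths, one can argue that the sentences cover different patients, because baseline counts as an evaluable visit in one and not in the other. But two missed visits from baseline make baseline the last evaluable visit, and the same patient has no evaluable follow-up visit. The offset arithmetic does depend on reading baseline as the scan date. If it means randomisation, the negative PFS time disappears and the mismatch between the 112-day sentence and BOR shrinks to 7 days.

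The reach is narrow. After approval of protocol version 2.0, Group A has no tumour scans. Days 233–273 arise only from unscheduled or out-of-window scans, or from a delay between randomisation and first dose. The worked week-48 event lies beyond both PFS landmarks. All of this stands, and it limits the impact without making the bounds correct.

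**Conclusion.** The point holds and is minor. Day 287 is wrong as the start of the 21-week band. The week-49 clause has two readings that give different PFS and DoR for the same patient. The 112- and 119-day limits conflict for a patient with only a baseline scan, and the start dates in 3.2.1 and 3.2.5 are not aligned.

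The band errors act mainly on the Kaplan-Meier curve after month 12 (day 365.25) and on DoR. The early-death conflict can move APF6 by 3.3 to 7.1 points for one patient, under the stated assumptions on arm size, other events and censoring. It can also make PFS and BOR disagree for that patient. PFS is exploratory and descriptive in 29 patients, and the SAP does not show that anyone falls in these bands.

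**What to change.** In 3.2.1, define the bands by the study day of the previous assessment:

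- before day 274: 17 weeks;
- days 274–329: 21 weeks;
- day 330 onwards: 25 weeks.

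Use one early-death limit of 119 days from randomisation in both sentences. Censor patients with no evaluable visit or no baseline data at randomisation (day 1). In 3.2.5, count both 17-week branches from randomisation.

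Check: after an on-time scan and one missed visit, the next scan comes at 112, 140 or 168 days if on time, and at 119, 147 or 175 if 7 days late. All are within the limits of 119, 147 and 175. For in-window scans, any first day from 233 to 274 for the 21-week band and from 289 to 330 for the 25-week band would work, so bounds that keep the SAP's week-plus-7-days convention (17 weeks through day 232, 21 weeks through day 288) are equally valid there. Days 274 and 330 also place unscheduled scans by their next two visits, and they classify every in-window scan correctly if first dose is 0 to 41 days after randomisation.

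One limit remains. The single 7-day allowance is kept, so a scan 7 days early followed by one 7 days late (126, 154 or 182 days) still exceeds the limit by 7 days.

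The cost is SAP wording and programming constants; no new data are needed.

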3.2.2 Objective response rate (ORR)

ORR (per RECIST 1.1 as assessed by the investigator) is defined as the number and percentage of patients with measurable disease with at least 1 visit response of CR or PR. Summaries will be produced based on both unconfirmed and confirmed response, where the response is confirmed at least 4 weeks later. ORR will be based on all randomised patients. Therefore, data obtained up until progression, or the last evaluable assessment in the absence of progression, will be included in the assessment of ORR.

A subject who goes off treatment without progression to receive a subsequent anti-cancer therapy, and then responds (CR or PR), will not be included as a responder in the ORR.

3.2.3 Duration of response (DoR)

DoR (per RECIST 1.1 as assessed by the investigator) will be defined as the time from the date of first documented response (CR or PR) until the first date of documented progression or death in the absence of disease progression, whichever is earlier (i.e., date of PFS event or censoring – date of first response + 1). The end of response should coincide with the date of progression or death from any cause used for the RECIST 1.1 PFS endpoint).

The time of the initial response will be defined as the latest of the dates contributing towards the first visit response of CR or PR. If a patient does not progress following a response, then the corresponding DoR will be censored at the PFS censoring time. Summaries will be produced based on both confirmed and unconfirmed progression.

DoR will not be defined for those patients who do not have documented response.

3.2.4 Disease control rate (DCR)

DCR is defined as the percentage of subjects who have a best overall response of CR or PR or SD at ≥ 4 weeks, prior to any PD event. Summaries will be produced based on both confirmed and unconfirmed response.

A subject's best overall response is calculated as defined below.

3.2.5 Best overall response

Best overall response (BOR) is calculated based on the overall visit response from each RECIST assessment. It is the best response a patient has had following randomisation but prior to starting any subsequent anti-cancer therapy and prior to RECIST progression or the last evaluable assessment in the absence of RECIST progression and subsequent anti-cancer therapy.

Categorisation of BOR will be based on RECIST using the following response categories: CR, PR, SD, PD and NE.

BOR will be determined programmatically based on RECIST from the overall visit response at each visit using investigator assessment data including all data up until the first progression,

the start of any subsequent cancer therapy or the last evaluable assessment in the absence of progression.

For determination of a best response of SD, the earliest of the dates contributing towards a particular overall visit assessment will be used. SD should be recorded at least 16 weeks +/- 1 week, i.e. at least 119 days (to allow for the assessment window), after randomisation (i.e. study day 120). For CR/PR, the initial overall visit assessment which showed a response will use the latest of the dates contributing towards a particular overall visit assessment.

For patients whose PFS event is death, BOR will be calculated based upon all evaluable RECIST assessments prior to death.

For patients who die with no evaluable RECIST assessments, if the death occurs ≤ 17 weeks (i.e., 16 weeks + 1 week to allow for a late assessment within the assessment window) after randomisation, then BOR will be assigned to the progression (PD) category. For patients who die with no evaluable RECIST assessments, if the death occurs > 17 weeks (i.e., 16 weeks + 1 week) after the date of first dose then BOR will be assigned to the NE category.

Progression events that have been censored due to them being more than two missed visits after the last evaluable assessment will not contribute to the BOR derivation.

Summaries will be produced based on both confirmed and unconfirmed response.

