4.1.2 Study day definitions

For the purpose of efficacy data summary, Study Day 1 is defined as the date of randomization to study treatment. For visits (or events) that occur on or after randomization, study day is defined as $(\text{date of visit [event]} - \text{date of randomization} + 1)$. For visits (or events) that occur prior to randomization, study day is defined as $(\text{date of visit [event]} - \text{date of randomization})$. There is no Study Day 0.

For the purpose of safety data summary, Dose Day 1 is defined as the date of first dose of study treatment (referred to in the protocol as Week 1 Day 1). For visits (or events) that occur on or after first dose, dose day is defined as $(\text{date of visit [event]} - \text{date of first dose of study treatment} + 1)$. For visits (or events) that occur prior to first dose, dose day is defined as $(\text{date of visit [event]} - \text{date of first dose of study treatment})$. There is no Dose Day 0.

For listings (such as for AEs) that include the derivation of “days since last dose,” this is defined as $(\text{event date} - \text{date of last dose})$. Events that occur on the same day as the last dose of study drug will therefore be described as occurring zero days from the last dose of study drug.

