4.2.7.7 DCR

DCR will be presented as the proportion of patients with disease control, out of the number of patients available per treatment arm. The associated 95% confidence intervals will also be provided using the Clopper-Pearson exact method for binomial proportions.

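### SAP 3.2.5 sets the minimum for stable disease at the late edge of the week-16 window (119 days), so on-time week-16 scans can fail a rule meant to admit them

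*SAP*

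**What the plan says.** Section 3.2.5 (Best overall response) gives the time condition for a best response of SD: "SD should be recorded at least 16 weeks +/- 1 week, i.e. at least 119 days (to allow for the assessment window), after randomisation". It restates this limit as study day 120. For dating an SD visit, "the earliest of the dates contributing towards a particular overall visit assessment will be used".

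The clocks are defined elsewhere. Section 4.1.2, for efficacy data: "Study Day 1 is defined as the date of randomization to study treatment". Section 3.1 schedules the scans from a different origin: "objective tumour assessments every 8 weeks (relative to the first dose) for the first 48 weeks, then every 12 weeks thereafter".

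Seventeen weeks appears in two other rules. For deaths with no evaluable assessment, 3.2.5 explains it as "16 weeks + 1 week to allow for a late assessment within the assessment window". In the PFS censoring rule of 3.2.1, "two missing visits will equate to 17 weeks (2 x 8 week scans + 7 day visit window").

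Section 3.2.4 defines disease control through a "best overall response of CR or PR or SD at ≥ 4 weeks, prior to any PD event", and refers to 3.2.5 for how best overall response is calculated. Section 4.2.7.7 adds: "DCR will be presented as the proportion of patients with disease control, out of the number of patients available per treatment arm", with Clopper-Pearson intervals.

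**The concern.** An allowance for a visit window should loosen a limit. For an upper limit that means adding the week; for a lower limit it means subtracting it. The SD rule is a lower limit, yet its figure is 16 weeks plus one week. The rule is therefore stricter than 16 weeks, although its wording says the week is there to accommodate the window. The other two 17-week rules are late limits, where adding is right.

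Best overall response is derived by program, so the constant will be coded as written. Consider a patient with SD at weeks 8 and 16 and progression at week 24, every scan on schedule. That patient could be denied a best response of SD, and would also leave DCR if the 3.2.5 rule carries over. A later SD scan would rescue the patient, but 3.1 and 3.2 end tumour scans for Group A once protocol version 2.0 is approved, so some patients may have no later scan.

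There is a linked ambiguity in 3.2.4. Its four-week condition has no effect if SD already needs 119 days. If it is meant to replace that minimum, the text does not say so.

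**Working it through.** **Inputs**
- SD minimum: 119 days after randomisation, study day 120 (3.2.5).
- Scans every 8 weeks from first dose (3.1), so the week-16 scan is due 112 days after first dose.
- Window: 7 days either side (the plus-or-minus one week in 3.2.5; the 7-day visit window in 3.2.1).
- Study day = days after randomisation + 1 (4.1.2).
- Gap g from randomisation to first dose: not given, so a range is shown.

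**The plan's own figure**
- 16 × 7 = 112, and 112 + 7 = 119 days, which is study day 120. The two stated forms agree with each other, and the figure comes from adding the window.
- Day convention check against 3.2.1: 32 × 7 + 7 + 1 = 232, as stated there.
- The early edge is 112 − 7 = 105 days, study day 106.

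**Which week-16 scans pass**

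A scan d days after first dose falls d + g days after randomisation. It qualifies if d + g ≥ 119. In-window scans have d = 105 to 119, which is 15 days. Excluded days = 14 − g for g = 0 to 14. The on-time scan (d = 112) passes only if g ≥ 7.

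| Gap g (days) | On-time scan, days after randomisation | On-time scan passes? | Window days excluded, of 15 |
|---|---|---|---|
| 0 | 112 | no | 14 |
| 3 | 115 | no | 11 |
| 6 | 118 | no | 8 |
| 7 | 119 | yes | 7 |
| 10 | 122 | yes | 4 |
| 13 | 125 | yes | 1 |
| 14 | 126 | yes | 0 |

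These are calendar days, not a share of scans. For g = 0 to 6 the first on-time scan that can support SD is week 24, at 168 + g days. An assessment spread over several days is tested at its first day, because SD takes the earliest contributing date.

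With a 105-day minimum, d + g ≥ 105 holds for all 15 window days at every g ≥ 0.

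**Effect on DCR**
- If the 3.2.5 minimum governs, one reclassified patient moves an arm's DCR by 100/n points. Assuming 29 patients split 14 and 15, this is 1/15 = 6.7 or 1/14 = 7.1 points.
- Four weeks is 28 days, below both 105 and 119, so the 3.2.4 condition is redundant if 3.2.5 applies.
- If four weeks governs instead, a week-16 scan meets it easily. DCR then does not change, and only the split of best response categories does.

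**The case against.** The operative limit is stated twice, in days and as a study day, and the two agree. Two programmers would code the same rule, and no sum is wrong: the fault lies in the direction of the allowance. The SAP nowhere states 105 days, and a deliberate 17-week minimum cannot be ruled out from this document. The other 17-week rules suggest where 119 may have come from, but not what was intended for SD.

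The effect also depends on an unknown gap and disappears at 14 days. Affected patients must have no complete or partial response, SD at a week-16 scan that falls short of 119 days, and no later SD scan. There may be none. The arm sizes are assumed, and a less even split would widen the percentage-point range. The four-week clause in 3.2.4 is a separate question. Finally, efficacy here is exploratory, with no hypothesis testing.

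Most of this stands as a limit on size and on certainty about the replacement value. It does not rescue the sentence. If 17 weeks was intended, the plus-or-minus and the stated reason are wrong; if the reason is right, the number is wrong. Consistent coding of 119 days would only apply the stricter limit to everyone.

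**Conclusion.** The point holds: as written, the SD minimum contradicts its own stated purpose. That conclusion is firm. That 105 days was meant is an inference from the wording and needs the protocol to confirm it.

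The consequence is conditional. With first dose 0 to 6 days after randomisation, an SD scan done exactly at week 16 does not count. At 7 to 13 days only early in-window scans are lost, 7 down to 1 of the 15 days. The number of patients affected cannot be derived from the SAP. The outputs at risk are best overall response and, only if the 3.2.5 rule governs it, DCR. ORR, PFS, OS, DoR and the primary safety objective are untouched. The correction should be made because the programmed result would be wrong for patients scanned on schedule, but it is not critical to the study's conclusions.

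**What to change.** Check the protocol for the intended SD minimum, then make the words and the number in 3.2.5 agree:

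- If the window is to be allowed for: at least 105 days (16 weeks minus 7 days) after randomisation, study day 106.
- If 17 weeks is truly intended: keep 119 days and study day 120, and delete the plus-or-minus one week and the parenthetical reason.

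In 3.2.4, state one SD minimum for DCR: delete the four-week condition, or say that it replaces the 3.2.5 minimum for this endpoint.

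The cost is two or three lines of SAP text and at most one programming constant.

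### DoR has no cut at subsequent anti-cancer therapy, so it can include a patient whom ORR counts as a non-responder; the BOR sentence on deaths leaves a related ambiguity

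*SAP*

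**What the plan says.** **ORR (SAP 3.2.2).** The rule is explicit: "A subject who goes off treatment without progression to receive a subsequent anti-cancer therapy, and then responds (CR or PR), will not be included". The exclusion is from the ORR numerator.

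**DoR (SAP 3.2.3).** DoR "will be defined as the time from the date of first documented response (CR or PR) until the first date of documented progression or death". The only patients left out are those with no documented response. The end of DoR is tied to the PFS event. SAP 4.2.7.6 describes the summarised group as patients with an initial response on study. Neither section mentions subsequent therapy or the ORR responder set.

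**BOR (SAP 3.2.5).** The definition reads "It is the best response a patient has had following randomisation but prior to starting any subsequent anti-cancer therapy and prior to RECIST progression". The programming rule then stops the data at the first progression, "the start of any subsequent cancer therapy or the last evaluable assessment in the absence of progression". A later sentence says "For patients whose PFS event is death, BOR will be calculated based upon all evaluable RECIST assessments prior to death", with no mention of subsequent therapy.

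**DCR (SAP 3.2.4).** It is taken from BOR: "DCR is defined as the percentage of subjects who have a best overall response of CR or PR or SD at". The minimum that follows there is 4 weeks. SAP 3.2.5 sets a different minimum for a best response of SD, at least 119 days after randomisation.

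**Tumour shrinkage (SAP 3.2.6).** Best percentage change uses only assessments before progression or the start of subsequent therapy.

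**The concern.** ORR, the general BOR rule and best tumour shrinkage all stop at the start of another anti-cancer therapy. DoR is the response endpoint without that stop, and the omission looks unintended. A response that first appears on the next therapy would then be described as a duration of response in the randomised arm. The number of patients in the DoR summary could also exceed the number of responders in the ORR table, which a reader of the study report could not explain.

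The second matter is one of wording. The sentence on deaths in 3.2.5 sits among special rules for patients who die, and a programmer could take it as a specific rule that replaces the general cut. BOR is derived by program and DCR is taken from it, so the choice would reach the tables.

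**Working it through.** The SAP gives no figure on this point, so there is nothing to reproduce. The check is whether the situation can arise and how each rule then classifies the patient.

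**Can the data exist?** Yes. SAP 3.1 has scans continuing before protocol version 2.0 whatever the reason for stopping study drug and despite later therapy. SAP 3.2.1 counts progression or death as a PFS event even after another anti-cancer therapy, and DoR ends at that event.

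**A constructed patient (assumed values).** Days are counted from randomisation as Day 1:
- Day 57: SD
- Day 100: subsequent anti-cancer therapy starts, without progression
- Day 113: NE
- Day 170: first PR
- Day 220: death, no progression recorded

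The death is not censored for missed visits. It comes 220 − 170 = 50 days after the last evaluable scan, well under the 17 weeks (119 days) in SAP 3.2.1.

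**ORR.** The first PR (Day 170) follows the new therapy (Day 100). The patient is not a responder.

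**DoR.** The first documented response is on Day 170 and the PFS event on Day 220. With the SAP's formula, event date − first response date + 1:

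DoR = 220 − 170 + 1 = 51 days.

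So the patient enters DoR and is absent from the ORR numerator.

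**BOR.** Under the general rule only the SD on Day 57 precedes the therapy, so there is no CR or PR. If the sentence on deaths overrides that rule, the visits are SD, NE and PR, and BOR is PR.

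**DCR.** The SD falls 57 − 1 = 56 days (8 weeks) after randomisation. That meets the 4-week wording of 3.2.4 but not the 119-day minimum of 3.2.5.

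| Reading of the sentence on deaths | CR/PR as BOR | Disease control, 4-week SD | Disease control, 119-day SD |
|---|---|---|---|
| Stays within the therapy cut | No | Yes | No |
| Overrides the therapy cut | Yes (PR) | Yes | Yes |

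The reading of the sentence always changes BOR for this patient. It changes DCR only in the last column.

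**After the fix.** With one cut applied throughout, the patient is an ORR non-responder, has no CR or PR as BOR, and is absent from DoR. DCR then depends only on which SD minimum applies.

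**The case against.** A reader might infer that BOR for patients who die plainly lacks the therapy cut, and hence that DCR counts responders whom ORR rejects. The SAP does not support that. Section 3.2.5 states the cut twice, "prior to starting any subsequent anti-cancer therapy and prior to RECIST progression" being the first, and exempts nobody. The sentence on deaths has a natural narrower meaning: a death does not by itself turn BOR into PD, and the scans before it still count. The sentences after it, on deaths with no evaluable scan, fit that meaning. This objection stands: what remains in 3.2.5 is an ambiguity. It is still worth closing, because on the narrower meaning the sentence adds little to the general rule, which invites the other reading.

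A reader might also want to attach a percentage-point shift to DCR. That is not supported either, because the shift is zero if SD at 4 weeks already counts as disease control.

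The scenario is narrow. The patient must stop without progression, start another therapy, be scanned on it and respond there for the first time. For the BOR question the patient must also die without recorded progression and without two missed visits. After protocol version 2.0 the scope shrinks further: Group A has no tumour scans, and Group B is scanned only to progression or for 3 months after discontinuation. Post-discontinuation therapies are summarised and listed (SAP 4.2.5.1), so an affected patient could be found. All of this limits the size of the problem, but none of it supplies the missing restriction in 3.2.3 or 4.2.7.6.

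**Conclusion.** The DoR definition is wrong as written, because it is inconsistent with ORR: it can admit a patient whom 3.2.2 says "and then responds (CR or PR), will not be included as a responder in the ORR". The sentence on deaths in 3.2.5 is a separate and weaker matter, an unresolved wording conflict that could change a BOR category and, under one of the two SD minima, DCR.

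Severity is minor. Each patient who fits adds one duration to the DoR summary. The SAP does not give the number of responders, so no effect on the median is claimed. Efficacy is an exploratory objective (SAP 1.1), only 29 patients were randomised, no hypothesis is tested (SAP 4), and the primary objective, safety, is untouched. The conclusion rests on the SAP's wording alone. The example's dates are assumed, and nothing in the SAP shows that any patient has this history.

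**What to change.** - **SAP 3.2.3**, with 4.2.7.6 to match: *DoR is defined only for patients counted as responders in ORR, from the first CR or PR before the start of any subsequent anti-cancer therapy.* Since 3.2.2 reports both unconfirmed and confirmed response, say which of the two defines the DoR group in each summary.
- **SAP 3.2.5**: at the end of the sentence on patients whose PFS event is death, add *and prior to the start of any subsequent anti-cancer therapy.*

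The end of DoR need not change; it can stay tied to the PFS event.

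The cost is two clauses of wording and a filter in the DoR program. The therapy start date is already needed for ORR and BOR, so no new data are required.
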